### Qualitative Interviews

Qualitative interviews conducted by a researcher who is part of the study team during the 12-month follow-up visit will be transcribed to text. A computer-assisted qualitative data analysis software package will be utilized to assist in thematic content analysis of the interview transcripts. A member of the research team will code the interviews for content, to identify emerging themes and organize data into thematic constructs utilizing a grounded theory approach. Descriptive statistics will be calculated for emerging themes.

### **8.9.4 Safety Analyses**

The primary measure of safety will be the reporting of adverse events. The Adverse events considered are Treatment Emergent Adverse Events (TEAE) defined as those AE's that occurred after dosing and those existing AEs that worsened during the study. Verbatim terms on case report forms will be mapped to preferred terms and system organ classes using the MedDRA dictionary. For incidence reporting if a subject has more than one adverse event mapped to the same preferred term, that adverse event will be reported only once using the highest severity and closest relationship to study drug. In separate columns, the overall frequency of AE's will be reported. Subject incidence of adverse events will be displayed by treatment group and by system organ class. Adverse events will also be summarized by severity and relationship to study drug. Subject incidence of serious adverse events by treatment group will also be displayed. In addition to the listing of all adverse events, a listing of serious adverse events and a listing of adverse events leading to discontinuation of study drug will be included.

Summary tables of frequency listings of expected adverse events (Spontaneously Reported Reactions) mapped to preferred terms will be displayed during and after each experimental session by condition.

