When each subject completes the evaluation at the primary endpoint, the blind will be broken for that subject. Subjects who had been assigned to receive low dose or medium dose MDMA will subsequently have the opportunity to enroll in the open-label study arm, or “Stage 2.” Stage 2 must start within a maximum of 5 months after the subject finishes Stage 1. The open-label study arm will follow a similar sequence of events and procedures, except that there will be a single preparatory session, and all three MDMA-assisted psychotherapy sessions will be open-label. Subjects will receive an initial dose of 100 mg MDMA in the first experimental session, and one of two active doses of MDMA that are clinically titrated by the CI during the second and third open-label experimental sessions that will otherwise follow the same sequence of events (See Time and Events Table). Outcome measures except for the NEO PI will be repeated one month after the second Stage 2 experimental session, and all outcome measures will be repeated at the end of Stage 2.

The study will conclude with a one-year follow-up occurring 12 months after the final experimental session of Stage 1 for subjects who received full dose MDMA or who elected not to enroll in Stage 2 after receiving either the medium or low doses in Stage 1. Subjects who enrolled in Stage 2 will have their final follow-up 12 months after the final open-label experimental session. Outcome measures will be repeated at the 12-month follow-up, as well as a questionnaire concerning self-reported long-term effects of study participation.

Sub-studies in a select group of subjects in this study may be conducted for exploratory purposes. Subjects will complete a separate consent process if they chose to participate in these studies.

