## 8.1 Analysis Populations

*Intent-to-treat (ITT)*: all subjects who were randomized

*Per protocol (PP)*: all subjects who completed Stage 1, underwent assessment of PTSD symptoms, and did not experience a major protocol deviation

*Crossover*: all subjects who completed Stage 2 in addition to completing Stage 1

*Safety*: all subjects who receive any study treatment

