## **8.6 Subject Disposition and Dosing Summary**

All subjects enrolled in the study (i.e., who sign informed consent and complete inclusion/exclusion criteria) will be included in the summary of subject disposition and accountability. No inferential statistical tests will be performed. The tabulation of number of subjects in each treatment group and overall will be displayed for all subjects who are randomized and had any treatment exposure, in the Safety Population, in the ITT Population, and in the PP Population. The number and percent of subjects who completed or discontinued the study will be displayed for each treatment group and overall together with reasons for early termination, where the percent is with respect to the total number of randomized subjects in that treatment group. The timepoint of doses and total MDMA (mg) administered will be summarized by treatment group for the Safety, ITT and PP Populations.

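### Adverse event, serious adverse event and total-MDMA summaries are laid out by treatment group with no stage split, so open-label 100-125 mg sessions fall, on the natural reading, under the 30 mg and 75 mg arms

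*SAP*

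**What the plan says.** SAP 8.9.4 makes adverse event reporting the main safety measure. Treatment-emergent events are "defined as those AE's that occurred after dosing and those existing AEs that worsened during the study". No end to that window is given at unblinding, at visit 13 or at the start of Stage 2. The layout is "Subject incidence of adverse events will be displayed by treatment group and by system organ class", and for serious events, "Subject incidence of serious adverse events by treatment group will also be displayed". Where a subject has repeat events under one preferred term, "that adverse event will be reported only once using the highest severity and closest relationship to study drug".

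The Safety population in SAP 8.1 is "all subjects who receive any study treatment", which does not exclude Stage 2 treatment. On exposure, SAP 8.6 says: "The timepoint of doses and total MDMA (mg) administered will be summarized by treatment group for the Safety, ITT and PP Populations".

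Under SAP 4.0, low- and medium-dose subjects may enter Stage 2 after unblinding and have three open-label sessions: "Subjects will receive an initial dose of 100 mg MDMA in the first experimental session", then 100 or 125 mg initial doses in sessions 2 and 3 (SAP Table 4.0-2). Protocol 6.2.10 collects and reports Stage 2 adverse events as in Stage 1. Protocol 12.0 promises frequency tables of adverse events and gives no rule for assigning them to a stage.

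**The concern.** The trial compares three doses, and Protocol 4.3 says they were chosen to help build a dose-response curve. A 30 mg column that also holds up to three sessions at 100-125 mg does not describe the safety of 30 mg. It also raises the comparator rate against which 125 mg is judged. The once-per-term rule compounds this: a severe event in Stage 2 replaces a mild event of the same term from a blinded 30 mg session and is shown under the 30 mg arm. SAP 8.10 places the primary efficacy analysis after Stage 2 is complete, so if the safety tables are run then or later, Stage 2 events will be in the data.

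**Working it through.** **Which group do Stage 2 data belong to?** No section defines treatment group. Three places show the SAP's usage. SAP 8.9.2.2 describes the crossover subjects as the 30 mg and 75 mg group when it compares Stage 2 visits. Its long-term follow-up paragraph attaches the 30 and 75 mg labels to visit 33, the end of Stage 2. SAP 8.9.3.1 (perceptions of sessions) analyses the 30 mg and 75 mg groups on Stage 2 data. Where the SAP wants dose received it says so: SOCQ scores are compared by initial dose for each session. A programmer following the text would put Stage 2 events in the randomised columns.

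**Doses per session.** Initial dose, up to initial plus supplement, reproduces SAP Tables 4.0-1 and 4.0-2: 30-45, 75-112.5 and 125-187.5 mg in Stage 1; 100-150 mg in Stage 2, or 125-187.5 mg with titration.

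**Exposure per subject completing every session.**
- Blinded Stage 1, two sessions: low 2 × (30 to 45) = 60-90 mg; medium 2 × (75 to 112.5) = 150-225 mg; full 2 × (125 to 187.5) = 250-375 mg.
- Stage 2: minimum 3 × 100 = 300 mg; maximum 150 + 2 × 187.5 = 525 mg.
- Pooled: low 360-615 mg; medium 450-750 mg; full 3 × (125 to 187.5) = 375-562.5 mg.

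Like for like (low / medium / full, mg):

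| Case | Low | Medium | Full |
|---|---|---|---|
| Initial doses only, no titration | 360 | 450 | 375 |
| Initial doses only, both later sessions titrated | 410 | 500 | 375 |
| All supplements, no titration | 540 | 675 | 562.5 |
| All supplements, both later sessions titrated | 615 | 750 | 562.5 |

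Medium exceeds full in all four cases; low exceeds full in the two titrated ones.

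**Observation time.** Protocol 8.3 collects all adverse events on the session day and for seven days after, so 8 days per session: 5 × 8 = 40 days for a crossover subject and 3 × 8 = 24 days for a full-dose subject.

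**Event incidence (illustration).** The documents give no per-session event rates and no crossover uptake. I assume a probability p per session at each dose and independent sessions. Blinded incidence is 1 − (1 − p)². With p_A the active-dose probability, pooled incidence in a crossover subject is 1 − (1 − p)²(1 − p_A)³, and in the full arm 1 − (1 − p_A)³. With crossover fraction u, a low or medium column shows u × pooled + (1 − u) × blinded. For p = 5/10/20%, the low arm gives 1 − 0.95² = 9.8% blinded and 1 − 0.95² × 0.8³ = 53.8% pooled; the full arm gives 36.0% over two sessions and 1 − 0.8³ = 48.8% over three.

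| Assumed p, low/medium/active | Blinded Stage 1 | Pooled, u = 50% | Pooled, u = 100% |
|---|---|---|---|
| 2/5/10% | 4.0/9.8/19.0% | 17.0/22.0/27.1% | 30.0/34.2/27.1% |
| 5/10/20% | 9.8/19.0/36.0% | 31.8/38.8/48.8% | 53.8/58.5/48.8% |
| 10/20/40% | 19.0/36.0/64.0% | 50.8/61.1/78.4% | 82.5/86.2/78.4% |

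**Uptake needed for reversal.** Setting the column equal to the full arm gives u = (full − blinded)/(pooled − blinded). In the 5/10/20% case: low (48.8 − 9.8)/(53.8 − 9.8) = 0.89; medium (48.8 − 19.0)/(58.5 − 19.0) = 0.75. Across the three rows: low 0.89 to 0.94, medium 0.71 to 0.85. Five of six is 0.83, so the low arm reverses only if all six cross over; the medium arm needs five of six in the first two rows and all six in the third.

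**Low uptake.** The full-dose column gains its own open-label third session. The gap to low dose equals the blinded gap when u = (48.8 − 36.0)/(53.8 − 9.8) = 0.29 in the 5/10/20% case. Below that uptake, pooling widens the gap.

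**The case against.** The SAP is silent rather than explicit: no sentence says that Stage 2 events count under the randomised arm, and a separate Crossover population exists in SAP 8.1. That stands as a limit on certainty. But the Crossover population is not named for the adverse event tables or the exposure summary, and the SAP's own labelling points to the randomised arm.

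The SAP 8.6 sentence also covers the timepoint of doses, so exposure might be shown by session. The wording is open on this; it states no stage split for the total.

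Much dose-related safety stays visible. Expected reactions are shown for each session by condition, C-SSRS and distress scores by time period, and vital signs by time point. This stands and narrows the point to treatment-emergent events, serious events and total MDMA. Listings of all adverse events and of serious ones would let a reader reconstruct matters in 24 subjects, but they do not correct the summary table.

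A reader might infer that the table will make full dose look no worse than low dose. The documents do not support that. Stage 2 is optional, reversal needs near-complete uptake, and the rates are assumed. If the same susceptible subjects reacted at every session, full crossover would bring every arm to the active-dose rate: the gradient would be lost, not reversed. No test of adverse event incidence is planned and the arms hold 6, 6 and 12 subjects, so no formal decision rule is affected.

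**Conclusion.** The point holds for three outputs: treatment-emergent event incidence, serious event incidence and total MDMA. It rests on reading treatment group as the randomised arm, the natural but not the stated meaning.

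The exposure distortion needs no assumed rates. For subjects completing all sessions it follows from the documents' own doses: the ordered blinded totals become overlapping pooled totals, and medium exceeds full in every like-for-like case.

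The effect on event incidence is conditional. In the 5/10/20% illustration the low-to-full gap falls from 26 points in blinded Stage 1 (36.0 − 9.8) to 17 at 50% uptake (48.8 − 31.8), with the order kept. The gradient can vanish or reverse only at high uptake: roughly above 70-85% for the medium arm and 89-94% for the low arm, given those rates and independent sessions. At any uptake the table mixes blinded and open-label periods and unequal numbers of sessions, so it cannot be read as a comparison of doses.

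**What to change.** In SAP 8.9.4 and 8.6, define treatment group and present treatment-emergent events (incidence, severity, relationship), serious events and MDMA exposure in four blocks:

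- (a) Blinded Stage 1, first dose to visit 13, by randomised arm. This is the only between-dose comparison.
- (b) Open-label session 3 in the full-dose arm, visits 14 to 18.
- (c) Stage 2, descriptive, showing dose received. No inference between doses, because titration is not randomised.
- (d) Long-term follow-up, limited to the event types still collected then.

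Apply the once-per-preferred-term rule within each block, and give the number of sessions or subject-days beside each incidence. An all-study listing can remain without a between-arm reading.

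The cost is SAP wording and extra table shells; no new data and no change to study conduct. The downside is more and smaller tables, with 6, 6 and 12 subjects in block (a) if all are dosed as planned, before any replaced subjects are added.

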### Columbia Suicide Severity Rating Scale (C-SSRS)

Suicidal ideation and behavior will be summarized according to suggestions made in the Columbia-Suicide Severity Rating Scale Scoring and Data Analysis Guide [3]. A positive response for suicidal ideation is counted when a subject answers "yes" to any one of the five suicidal ideation questions (Categories 1-5) on the C-SSRS, i.e. a score > 0 for suicidal ideation score. Serious suicidal ideation is a suicidal ideation score of 4 or 5. A positive response for suicidal behavior occurs when a subject answers "yes" to any one of the five suicidal behavior questions (Categories 6-10) on the C-SSRS, i.e. a score > 0 for suicidal behavior score. The number and percent of positive responses of Positive Ideation, Serious Ideation, and Positive Behavior will be tabulated by treatment group and time period. P-values will be calculated using the chi-squared test for overall treatment group differences and Fisher's exact test will be used for pairwise testing. Compare lifetime serious suicidal ideation and positive behavior frequencies to cumulative frequencies anytime during the study until end of stage 1 and stage 2 using chi-squared test for overall treatment group differences and Fisher's exact test for pairwise testing.

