At approximately 10:00 A.M., participants will receive the initial dose of MDMA along with a glass of water. The participant will sit or recline on comfortable furnishings, and there will be eyeshades and headphones if the participant wishes to use them. They will listen to a program of music designed to support their experience by initially aiding relaxation and later evoking and supporting deep emotions and the emergence of unconscious material [99, 100]. They may also request periods of music if they wish. The investigators will also encourage periods of time in which the participant remains silent with eyes closed and with attention focused inward in order to allow for the further unfolding of their inner experience, in accordance with the principles of MAPS' treatment manual [101]. Water and electrolyte containing fluids will be available ad lib throughout the session within the limits described in Appendix A. Food will be available during the latter part of the session. The investigators may record the entire session to video and audio. Participants may receive a copy of audio or video recordings of at least one experimental session upon request. The participant will be encouraged to spend much of the time focusing attention on their inner experience without talking, but may speak to the investigators whenever they wish, and will receive guidance and support as needed. After the first hour, if the participant has not spoken spontaneously, the investigators will check in with him/her about the nature of the experience. For the rest of the experience, as appropriate, the investigators will support and encourage the participant in emotional processing and resolution of whatever psychological material is emerging.

Suicidality will be assessed with the C-SSRS twice during each experimental session (approximately one hour before and five to six hours after drug administration).

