# 6.2.4 Integrative Sessions 24 Hours after Experimental Session [Visits 6, 10, 15 (15 for full dose group only)]

On the morning after the MDMA session, the participant will meet with both investigators during a 90-minute integrative psychotherapy session.

Adherence criteria for integrative sessions should be completed as a part of one of the three sessions following each experimental session. These elements do not have to be accomplished in any specific order or all in each and every integrative session. Generally, adherence criteria for these sessions include discussing material that emerged during experimental sessions and helping participants integrate their experiences both internally and into daily life. Therapists will emphasize their commitment to support the subject during the integration period and will be available via phone or pager. Subjects will be encouraged to relax and rest as much as possible for several days after the experimental session.

Participants will complete the C-SSRS during each integrative session. At the beginning of this session, the participant and both investigators conducting psychotherapy will indicate their beliefs concerning participant condition assignment. The participant and investigator will then discuss and review events, thoughts, feelings and memories that occurred during the experimental session. If necessary, the investigators will help the participant to reduce any residual psychological distress he or she may be experiencing. The therapists will also encourage exploration of any new insights and perspectives resulting from states of acceptance, feelings of intimacy, and reduced fear that may have occurred during MDMA sessions and that may be applicable to emotionally distressing

situations in everyday life. The investigators will be supportive, validating the MDMA experience and facilitating understanding and emotional clearing. The investigators will assess participant mental health and the presence of any remaining reactions during integrative psychotherapy sessions. Integrative psychotherapy sessions can also serve as an opportunity for the investigators to gather information in an unstructured manner about the effects of MDMA on the participant. If subjects who have pre-existing tinnitus or chronic pain mention any changes, the visual analog scale will be used to collect the changes in symptoms.

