# 6.2.5 Daily Telephone Contact for Seven days after an Experimental Session

Investigators will follow the most recent version of the Treatment Manual in all matters relating to follow-up subsequent to the experimental psychotherapy sessions. Starting on the day of the non-drug integrative psychotherapy session following each experimental session, one of the investigators will contact the participant via telephone daily for one week. The telephone contact will be for a brief check-in lasting 5 to 15 minutes, or as long as necessary to address any participant's concerns or difficulties integrating their experience and to assess participant well-being. Additional telephone contact can be initiated at the request of the investigators or participant. On the second and seventh day of telephone contact, the C-SSRS will be administered to monitor for suicide risk.

Adverse Events and medications will be collected as described in Sections 8 and 9 of the protocol.

If the investigators are unable to reach a subject by telephone despite repeated attempts, every effort will be made to contact their outside physician or a family member to be sure they receive any support needed. If the investigators eventually contact the person, this participant would be permitted to remain enrolled in the study only if measures could be put in place to assure that such a problem would not recur.

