## **8.0 Analyses**

In general, nominal variables will be described in terms of frequencies and percentages and analyzed using chi square analysis. Ordinal and non-normal continuous variables will be described using sample median and range, and analyzed by non-parametric statistical tests, and approximately normal variables will be described using sample mean and standard deviations and analyzed by parametric statistical tests. All statistical tests will be two-sided and a difference resulting in a p-value of less than or equal to 0.05 will be considered statistically significant. All p-values will be rounded to and displayed in four decimals. If a p-value less than 0.0001 occurs it will be shown in tables as <0.0001.

Clinical data will be presented in tabular format. Data not subject to analysis according to this plan will not appear in any tables or graphs, but will be included in the data listings.

Analyses will be carried out with SAS Version 9.3 or higher. Selected results may be presented graphically using standard graphical software.

Post-hoc exploratory analyses not identified in this SAP may be performed to further examine the study data. These analyses will be clearly identified as such in the final clinical study report.

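### The C-SSRS tests in SAP 8.9.4 count positive responses by an undefined time period; wherever a period holds more than one administration, one person's repeated answers are tested as if independent

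*SAP*

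**What the plan says.** The C-SSRS paragraph of SAP 8.9.4 sets the tabulation: "The number and percent of positive responses of Positive Ideation, Serious Ideation, and Positive Behavior will be tabulated by treatment group and time period". It continues: "P-values will be calculated using the chi-squared test for overall treatment group differences", with Fisher's exact test for pairs of groups. SAP 8.0 sets the threshold for all tests: "All statistical tests will be two-sided and a difference resulting in a p-value of less than or equal to 0.05". The C-SSRS paragraph gives no denominator for the percentages, no definition of the time period, and no rule for a subject who is positive more than once.

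The protocol makes repetition routine:
- Section 6.2.3: "Suicidality will be assessed with the C-SSRS twice during each experimental session".
- Section 6.2.4: "Participants will complete the C-SSRS during each integrative session". Protocol 5.0 and SAP 4.0 give three integrative sessions after each experimental session.
- Section 6.2.5: "On the second and seventh day of telephone contact, the C-SSRS will be administered to monitor for suicide risk".
- Section 6.2.6: an integrative session that falls within the seven days of calls replaces that day's call.

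The opening paragraph of SAP 8.9.4, on adverse events, handles the same issue explicitly. It reports subject incidence, counts a subject once per preferred term at the highest severity, and puts event frequency in separate columns.

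**The concern.** Both tests assume independent units. In this trial the independent unit is the subject, and there are 6, 6 and 12 of them. Suicidal ideation in one person over a few weeks is unlikely to be independent from one administration to the next. If several administrations per subject enter one table, the effective sample is smaller than the table suggests and the p-values are too small.

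Suicidality is a stated safety objective, with comparisons between conditions (Protocol 3.3, SAP 3.3). If the unit is left open, the person programming the table decides whether one subject's persistent ideation appears as one case or as a significant dose difference. That decision would be made when the data are already in hand.

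**Working it through.** The documents give no C-SSRS power, rate or p-value, so there is no stated figure to reproduce. The check is what the tests return under each reading of the text.

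**Inputs**
- Group sizes: low 6, medium 6, full 12 (SAP 5.0, evaluable subjects).
- Administrations per cycle: 2 on the session day + 3 integrative + 2 telephone = 7. If integrative sessions replace both telephone days, 7 − 2 = 5. As-needed administrations would add to this.
- Denominators if one seven-administration cycle is pooled: 6 × 7 = 42, 6 × 7 = 42 and 12 × 7 = 84, so N = 168. These are assumed for illustration and appear nowhere in the SAP.

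**Formulas**
Suppose all A positives fall in one arm with n units out of N.
- Pearson chi-squared: X² = [N² / (A(N − A))] × (A²/n − A²/N). With 2 degrees of freedom, p = exp(−X²/2).
- Two-sided Fisher, low v full, for the low-arm examples below: p = C(n_low, A) / C(n_low + n_full, A). No other table is as improbable.

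**One low-dose subject positive on 3 of 7, cycle pooled (3/42, 0/42, 0/84)**
- X² = [168²/(3 × 165)] × (9/42 − 9/168) = 57.02 × 0.1607 = 9.16; p = 0.010.
- Fisher low v full: (42 × 41 × 40)/(126 × 125 × 124) = 68,880/1,953,000 = 0.035.

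**The same data counted as subjects (1/6, 0/6, 0/12)**
- X² = [24²/(1 × 23)] × (1/6 − 1/24) = 25.04 × 0.125 = 3.13; p = 0.21.
- Fisher low v full: 6/18 = 0.33.

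**Other patterns, one positive subject**

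| Reading | Table (low, medium, full) | Chi-squared p | Fisher low v full p |
|---|---|---|---|
| Cycle of 7, low-dose subject, 2 of 7 | 2/42, 0/42, 0/84 | 0.048 | 0.109 |
| Cycle of 7, low-dose subject, 7 of 7 | 7/42, 0/42, 0/84 | < 0.0001 | 0.0003 |
| Five administrations, low-dose subject, 3 of 5 | 3/30, 0/30, 0/60 | 0.010 | 0.035 |
| Session day pooled, low-dose subject, 2 of 2 | 2/12, 0/12, 0/24 | 0.044 | 0.105 |
| Cycle of 7, full-dose subject, 3 of 7 | 0/42, 0/42, 3/84 | 0.22 | 0.55 |
| Cycle of 7, full-dose subject, 7 of 7 | 0/42, 0/42, 7/84 | 0.026 | 0.094 |
| Subject as unit, full-dose subject | 0/6, 0/6, 1/12 | 0.59 | 1.00 |

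The five-administration row also fits a period made up of the integrative and telephone contacts after a session (3 + 2 = 5).

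**Type I error.** This was simulated from a beta-binomial model with 20,000 runs and group sizes 6, 6 and 12. The positive rate (5% to 30%) and the within-subject correlation are assumptions, since the documents give neither. For the overall chi-squared test on seven pooled administrations, the error is about 4% to 5% at correlation 0, 21% to 26% at 0.2, and 42% to 50% at 0.5. With the subject as unit it is at most about 5.4%.

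**The case against.** The strongest reply is that the SAP never says administrations are pooled. Several features point to the subject as the unit:

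- The definition is worded around the person: "A positive response for suicidal ideation is counted when a subject answers" yes to any one of the five questions. That can be read as classifying a subject.
- SAP 8.5 uses a since-last-visit form after the lifetime assessment. Each administration covers its own interval, so one administration per period is a natural layout.
- The two session-day administrations are one before and one after drug (Protocol 6.1.2), and a safety table would normally keep them apart.
- The next comparison reads: "Compare lifetime serious suicidal ideation and positive behavior frequencies to cumulative frequencies anytime during the study until end of stage 1 and stage 2". Lifetime status is one value per subject, so this makes sense only as ever or never.
- The paragraph defers to a cited scoring guide, which may settle the unit. It is not available here, so it supports neither reading.
- Adverse events are the primary safety measure, no stopping rule depends on C-SSRS p-values, and the trial is a pilot.

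Much of this stands. If each period is one administration, responses equal subjects and the problem disappears. The lifetime comparison is sound on its natural reading. What remains is that the sentence carrying the p-values counts responses and leaves the period open, whereas the adjacent adverse-event text counts subjects once. The SAP should be executable from its own words.

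**Conclusion.** The point holds as a conditional defect that should be corrected. SAP 8.9.4 leaves the unit, denominator and period of the C-SSRS tests undefined. Any period with more than one administration gives invalid p-values if the sentence is followed literally. Depending on that unstated choice, one low-dose subject positive throughout a cycle gives an overall p of 0.21 or of less than 0.0001.

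Three stronger readings are tempting, and the documents do not support them:
- That the plan definitely tests responses instead of subjects. It names no pooling and no denominator.
- That exposure is overstated seven-fold. This is true only if a whole seven-administration cycle is one period, and the count per cycle can be as low as 5.
- That one subject can create a significant difference equally in either direction. A full-dose subject positive on 3 of 7 gives nothing near 0.05. At 7 of 7 only the overall chi-squared test crosses it; the pairwise Fisher test does not.

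The figures assume 6, 6 and 12 subjects, complete administrations and one positive subject. The type I error figures also rest on the assumed rates and correlations.

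**What to change.** In the C-SSRS paragraph of SAP 8.9.4:
1. Replace the count of positive responses with the number and percent of subjects with at least one positive response in the period, using the worst score in that period.
2. Use the subjects assessed in that period as the denominator.
3. Name the periods, keeping pre-drug and post-drug administrations separate.
4. Apply tests only to subject counts.
5. List every positive administration by subject, so that persistence within a person stays visible.

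The cost is a few sentences in the SAP and the matching table shell. The data are already scheduled for collection, and nothing is lost if subject counting was the intention.

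One related matter is not settled by this change: expected counts stay far below 5 even with subjects as the unit. For 2/6, 0/6, 0/12 the chi-squared p is 0.038, whereas the exact three-group p is 2 × C(6,2)/C(24,2) = 30/276 = 0.109. An exact overall test, or description only, would be safer.
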